6.4. Secondary Endpoints Analysis

The PPE will be used to analyze all secondary efficacy endpoints.

6.4.1. Key Confirmatory Secondary Endpoints

The following secondary endpoint will be formally analyzed:

1. First occurrence of any RT-PCR-confirmed RSV ARI, with onset at least 14 days after dosing of study vaccine
2. First occurrence of any RT-PCR-confirmed RSV-mediated LRTD during the second year, with onset after study Day 365
3. First occurrence of any RT-PCR-confirmed RSV ARI during the second year, with onset after study Day 365
4. First occurrence of predefined clinically relevant disease associated with RT-PCR-confirmed RSV-mediated ARI over the whole study, with onset at least 14 days after dosing of study vaccine

Formal inference for secondary endpoint 1 (RSV ARI) as part of the testing strategy will occur at the primary analysis, for secondary endpoints 2, 3 and 4 the formal inference as part of the testing strategy will only occur at study end (Table 10). Exploratory descriptive analyses of these endpoints might also occur at other planned analysis timepoints.

Note: Occurrence is always referring to the start of the ARI as reported in the CRF (CESTDTC). Second year starts at the study Day 365 visit, or relative day 365, in case Day 365 visit not available but there are ARI surveillance questions available after the relative day 365.

6.4.1.1. Definition of Endpoints

6.4.1.1.1. Case Definition for RT-PCR-confirmed RSV-mediated ARI

A participant will be considered to have RT-PCR-confirmed RSV-mediated ARI if the following criteria are met:

ARI episode reported by participant and confirmed by the site. See ‘*ARI episode definition*’ in Section 6.3.1.

Confirmation of RSV by RT-PCR in one or more of the nasal swabs, or in the sputum sample, when available. See ‘*RSV RT-PCR Confirmation of the Considered ARI Episode*’ in Section 6.3.1.

6.4.1.1.2. Predefined Clinically Relevant Disease Associated with RT-PCR-confirmed RSV-mediated ARI

A participant will be considered to have clinically relevant disease with specific parameters associated with an RT-PCR-confirmed RSV-mediated ARI if the following criteria are met:

The participant has an RT-PCR-confirmed RSV-mediated ARI as defined in Section 6.4.1.1.1.

Any of the following is associated with the ARI:

- **Hospitalization** (as collected on eCRF AE pages (linked via acute respiratory infection form or complications linked to ARI form), medical encounters [Intensive Care Unit and Hospital inpatient department] form and MRU pages [Emerging Hospitalization admissions (Emerging emergency department visits are not taken into account)])
- **Emergency department visit** (as assessed on the eCRF medical encounters form and MRU pages [emerging MRU to be summarized])
- At least one of the following **complications**: asthma, COPD, respiratory distress, bronchitis, bronchial hyperreactivity, CHF, cardiac arrhythmia, renal impairment or the presence of X-ray or radiological confirmed , respiratory arrest and/or failure, pulmonary embolism, pleural effusion, atelectasis, acute coronary events, acute cerebrovascular events, altered mental status, seizure, syncope, systemic inflammatory response syndrome (SIRS), new neurological deficit, asthenia, dehydration or metabolic disturbances.

See Section 7.8 for the complication terms. These terms will be reported in the AE or the CE domain.

Asthma and chronic obstructive pulmonary disease (COPD) exacerbation supporting LRTD reported in the medically attended ARI form will also be counted, as well as X-ray or radiological confirmed pneumonia from the diagnostic tests form.

- **Decreased oxygen saturation:**
Based on the vital signs form collected at the site: defined as oxygen saturation of <92% for participants with a baseline oxygen saturation of $\geq 92\%$ or missing at randomization; for participants with baseline oxygen saturation <92%, decreased oxygen saturation is defined as a $\geq 3\%$ decrease in their oxygen saturation from baseline
Based on eCRF pages on measurements during a medically attended ARI (eq. hospitalizations): defined as oxygen saturation of <92% supporting LRTD

- **Tachypnea** (at least emerging Grade 2, see respiratory rate at Section 7.6)
- Need of **supplemental oxygen** (as indicated on the eCRF medical encounters form, the eCRF oxygen supplementation form and from emerging MRUs [both ‘*Supplemental oxygen used?*’ and ‘*Mechanical ventilation used?*’ questions to be used])
- **Hypotension** (emerging Grade 3, see Section 7.6)
- **Pulmonary function test** results supporting diagnosis of LRTD (as captured under the eCRF pages on measurements during a medically attended ARI, where peak expiratory flow, spirometry FVC, FEV1 or FEV6 support diagnosis of LRTD)
- **Arterial blood gas** results supporting diagnosis of LRTD (as captured under the eCRF pages on measurements during a medically attended ARI, where arterial blood gas pH, pO₂, pCO₂, HCO₃ supports diagnosis of LRTD)

6.4.1.2. Level of Significance

The VE against the primary endpoint will be tested using the significance level α' (α_1 or α_2 or α_3 or α_4), as defined in Section 6.3.2. If the LL of the exact 2-sided CI ($1-2\times\alpha'$) for the VE (1-relative risk rate) calculated from the Exact Poisson regression model, is above 20% and the observed VE is above 50%, VE is demonstrated for the primary endpoint. If VE is demonstrated for the primary endpoint, the above secondary endpoints will be tested according to the testing order displayed in Table 10. The first secondary efficacy endpoint (first occurrence of any RT-PCR-confirmed RSV ARI) is tested using the same significance level α' as used for the primary endpoint. Exact 2-sided CIs ($1-2\times\alpha'$) for the VE (1-relative risk rate) will be calculated from these Exact Poisson regression models. If the LL of the CI is above 0%, VE will have been demonstrated for this endpoint and the next endpoint in the testing strategy can be tested. The following secondary endpoints (#2, #3 and #4) will be tested hierarchically at the end of the study at the full alpha ($\alpha=2.5\%$), as indicated in Table 10 below.

Table 10: Secondary Endpoints: Overview of the Testing Order, Timing of the Testing in the Testing Strategy and the Corresponding Alpha

Secondary endpoint: first occurrence of	Analysis timepoint in the testing strategy	Alpha at which the endpoint is tested
1. Any RT-PCR confirmed RSV ARI	Time of primary analysis	Alpha used at the primary analysis
2. Any RT-PCR confirmed RSV LRTD during the second Year	End of the study	2.5%
3. Any RT-PCR confirmed RSV ARI during the second Year	End of the study	2.5%
4. Predefined clinically relevant disease associated with RT-PCR-confirmed RSV-mediated ARI	End of the study	2.5%

Second year starts at the D365 visit

6.4.1.2.1. Analysis Methods

A similar Exact Poisson regression model as for the primary endpoint will be used for the analyses of the secondary endpoints focusing on VE.

For secondary endpoints focusing on VE during the second year, the follow up time will be defined as indicated below:

For participants with events occurring from the Day 365 onwards, the follow-up time is defined as the time between Day 365 study visit and the occurrence of the event. For participants with no events, the follow-up time is the time between Day 365 study visit and the minimum of the database cut-off date of the analysis and the completion or discontinuation date. Participants who discontinue prior to the Month 12/Day 365 visit and participants that have an MPD impacting efficacy during the first or second year are excluded from this analysis. For those secondary endpoints, each participant will be taken into account in the model with one observation indicating whether they had an event or not, the vaccination group, the stratification factors and the follow up time. Events with onset from the study Day 365 onwards will be considered in the model.

For the first occurrence of any RT-PCR-confirmed RSV ARI and first occurrence of predefined clinically relevant disease endpoints, refer to Section 6.3.3.

Note: Occurrence is always referring to the start of the ARI as reported in the CRF (CESTDTC). Second year starts at the study Day 365 visit, or relative day 365, in case Day 365 visit not available but there are ARI surveillance questions available after the relative day 365.

The proportion of participants meeting the different secondary endpoints, will also be summarized with the corresponding VE and will be depicted with forest plots.

6.4.2. Supportive (Non-Confirmatory) Secondary Endpoint

The AUC of the change from baseline in RiiQ Total Symptom score (see Section 6.6.7.1) in participants with an RT-PCR-confirmed RSV-mediated ARI over the whole study.

The AUC is calculated from the first symptoms reported after the start of the ARI (CESTDTC) until the end of the ARI (CEENDTC). See Section 7.9 for details on the calculations.

6.4.2.1. Analysis Methods

The AUC of the change from baseline in RiiQ Total Symptoms score from the ARI episode corresponding with the first occurrence of any RT-PCR-confirmed RSV-mediated ARI over the whole study, with onset at least 14 days after vaccination will be summarized.

Descriptive statistics will be calculated restricting to participants with RT-PCR confirmed RSV-mediated ARI during the whole study. A Wilcoxon Rank Sum test will be performed to test the null hypothesis that the distribution in both groups is the same versus the alternative hypothesis that the distribution shifted towards a lower AUC in the change from baseline in RiiQ Total Symptom score (ie, more reduced symptom scores) in the considered active group. This is a non-confirmatory endpoint and will not be taken into account in the testing strategy, no alpha correction will be applied.

6.5. Exploratory Endpoints Analysis

The PPE will be used to analyze all exploratory efficacy analysis. For the definition of RT-PCR confirmed RSV- mediated LRTD and ARI please refer to Section 6.3.1.

Moreover, RT-PCR confirmed Flu and hMPV- mediated LRTD and ARI are defined in the same way as the RSV- mediated LRTD and ARI, Section 6.3.1, but instead of an RSV confirmation a Flu or hMPV confirmation is required, respectively. The CEC will not evaluate the RT-PCR confirmed Flu and hMPV- mediated ARIs, therefore the LRTD definition will be based on the programmed definition. The following exploratory endpoints, will be analyzed:

- First occurrence of RT-PCR-confirmed RSV-mediated LRTD during the first year, with onset between 14 days post vaccination and Day 365.
- First occurrence of RT-PCR-confirmed RSV-mediated ARI during the first year, with onset between 14 days post vaccination and Day 365.
- First occurrence of RT-PCR-confirmed RSV-mediated LRTD by subtype (RSV A or RSV B), based on the DDL assay

Note: This is defined as an RT-PCR-confirmed RSV-mediated LRTD (see Section 6.3.1) in combination with the considered RSV subtype (RSV A or RSV B respectively) obtained from DDL in at least one of the samples taken up to 7 days after the onset of the ARI episode or during the ARI episode. Both nasal and sputum swabs will be taken into consideration.

- First occurrence of RT-PCR-confirmed RSV-mediated ARIs by subtype (RSV A or RSV B), based on the DDL assay

Note: This is defined as an RT-PCR-confirmed RSV-mediated ARI (see Section 6.4.1.1.1) in combination with the considered RSV subtype (RSV A or RSV B respectively) obtained from DDL in at least one of the samples taken up to 7 days after the onset of the ARI episode or during the ARI episode. Both nasal and sputum swabs will be taken into consideration.

First occurrence of complications associated with RT-PCR-confirmed RSV-mediated ARIs, RT-PCR-confirmed RSV-mediated LRTDs, influenza-mediated ARIs and hMPV-mediated ARIs. For the list of complications see corresponding bullet in Section 6.4.1.1.2.

- First occurrence of hospitalizations associated with RT-PCR-confirmed RSV-mediated ARIs, RSV-mediated LRTD, influenza-mediated ARIs and hMPV-mediated ARIs. See Section 6.4.1.1.2 for hospitalization definition.
- First occurrence of pneumonia (radiological or X-ray confirmed, as assessed in the CRF diagnostic tests form or reported as a complication) associated with RT-PCR-confirmed RSV-mediated ARIs, RSV-mediated LRTD, influenza-mediated ARIs and hMPV-mediated ARIs
- First occurrence of emerging therapeutic interventions of interest associated with RT-PCR-confirmed RSV-mediated ARIs, RSV-mediated LRTD, influenza-mediated ARIs and hMPV-mediated ARIs. The following are considered emerging therapeutic interventions of interest (Section 7.10) :
 - New onset or increased dose (compared to baseline) of bronchodilator/nebulizer treatment

- New onset or increased dose (compared to baseline) of corticosteroid prescription
- New onset or increased dose (compared to baseline) of antibiotic prescription
- New onset or increased dose (compared to baseline) of antiviral prescription

Note: These will be taken from the concomitant medication pages of the eCRF. The concomitant medications listed in Section 7.10 are considered as therapeutic interventions of interest. The principal investigator will indicate whether there has been new onset of increase in dose compared to baseline in the CRF. Those associated with an ARI or complication of an ARI will be displayed.

- First occurrence of RT-PCR confirmed hMPV-mediated ARI
- First occurrence of RT-PCR-confirmed hMPV-mediated LRTD
- First occurrence of RT-PCR confirmed influenza-mediated ARI and influenza-mediated LRTD
- First occurrence of an RT-PCR-confirmed RSV LRTD assessed as at least mild, as at least moderate and as severe by the CEC during the considered year:
 - with onset at least 14 days after dosing of study vaccine and prior to study Day 365 (first year comparison)
 - with onset from the study Day 365 onwards (second year comparison)
 - with onset at least 14 days after dosing of study vaccine (whole study comparison)

Note: Occurrence is always referring to the time to the start of the ARI as reported in the CRF (CESTDTC). The start of the associated ARI will also be used for calculating the time to first occurrence of emerging therapeutic interventions, pneumonia, complications and hospitalizations.

- First occurrence of RT-PCR-confirmed, RSV-mediated LRTD during the second year and over the whole study (if the primary analysis is conducted before the end of the study):
 - with onset from the study Day 365 visit onwards (second year comparison)
 - with onset 14 days after the first dose of study vaccine (whole study comparison)
- First occurrence of RT-PCR-confirmed, RSV-mediated ARI over the whole study (if the primary analysis is conducted before the end of the study), with onset at least 14 days after the first dose of study vaccine
- First occurrence of predefined clinically relevant disease associated with RT-PCR-confirmed RSV-mediated ARI and LRTD

Note: If the primary analysis occurs in 2022 exploratory endpoints related to the whole study (data collected up to Data base cut off) will be analyzed, and the first- and second-year endpoints will not be analyzed at that timepoint.

If the primary analysis occurs in 2023 all exploratory endpoints will be analyzed up to the date of the data base cut off.

The inclusion of Flu and hMPV endpoints in the primary or additional analyses is depending on the cleaning status of those cases at the time of analyses. They will be included in the end of study analysis.

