9.4.1.4. Exploratory Endpoints

For the following exploratory endpoints, similar Exact Poisson regression models as for the primary and secondary endpoints will be used and exact 2-sided 95% CIs for VE (1-relative risk rate) will be calculated. For all exploratory endpoints related to influenza-mediated ARI and LRTD only the proportion of participants meeting the respective endpoints will be summarized.

- First occurrence of RT-PCR-confirmed RSV-mediated LRTD during the first year
- First occurrence of RT-PCR-confirmed RSV-mediated ARI during the first year
- First occurrence of RT-PCR-confirmed RSV-mediated LRTD by subtype (RSV A or RSV B)
- First occurrence of RT-PCR-confirmed RSV-mediated ARIs by subtype (RSV A or RSV B)
- First occurrence of complications associated with RT-PCR-confirmed RSV-mediated ARIs RSV-mediated LRTD, influenza-mediated ARIs and hMPV-mediated ARIs
- First occurrence of hospitalizations associated with RT-PCR-confirmed RSV-mediated ARIs RSV-mediated LRTD, influenza-mediated ARIs and hMPV-mediated ARIs

- First occurrence of pneumonia (radiological or X-ray confirmed) associated with RT-PCR-confirmed RSV-mediated ARIs RSV-mediated LRTD, influenza-mediated ARIs and hMPV-mediated ARIs
- First occurrence of emerging therapeutic interventions of interest associated with RT-PCR-confirmed RSV ARIs. The following are considered emerging therapeutic interventions of interest:
 - New onset or increased dose (compared to baseline) of bronchodilator/nebulizer treatment
 - New onset or increased dose (compared to baseline) of corticosteroid prescription
 - New onset or increased dose (compared to baseline) of antibiotic prescription
 - New onset or increased dose (compared to baseline) of antiviral prescription
- First occurrence of RT-PCR-confirmed hMPV-mediated ARI
- First occurrence of RT-PCR-confirmed hMPV-mediated LRTD

Unless specifically mentioned otherwise, the Ves will be calculated for the above endpoints occurring during the first year, and during the second year and over the whole study. The follow-up time is determined in a similar way as for the primary and secondary endpoints.

If the primary analysis occurs before the end of the study, the secondary endpoints #2, #3 (provided second year data are already available) and #4 might be analyzed descriptively at the time of the primary analysis, VE with 95% CI will be calculated.

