10.6. Appendix 6: Medically-attended ARI Form

Section 1: To be completed in all healthcare settings (e.g., family doctor, nurse practitioner, outpatient clinic, emergency department visits and hospitalizations).

Participant ID (will be completed by study staff):
Date of visit:
Name and role of healthcare professional completing form:
Optional contact details:

DIAGNOSIS/DIAGNOSES
Please list diagnosis or diagnoses made during clinical interaction here.

MEDICATIONS
Please list any new medications prescribed or changes in medication dosing.

VITAL SIGNS
Temperature (°C/°F): _____
Respiratory rate (breaths per minute): _____
Does the measured respiratory rate support a diagnosis of lower respiratory tract disease (LRTD)?  Yes  No
Below question only to be completed if patient has history of COPD or asthma.
Does the measured respiratory rate support a diagnosis of a COPD or asthma exacerbation?  COPD exacerbation  asthma exacerbation  No
Oxygen saturation (SpO₂): _____
Does the measured oxygen saturation support a diagnosis of lower respiratory tract disease (LRTD)?  Yes  No
Below question only to be completed if patient has history of COPD or asthma.
Does the measured oxygen saturation support a diagnosis of a COPD or asthma exacerbation?  COPD exacerbation  asthma exacerbation  No
WERE ADDITIONAL DIAGNOSTIC TESTS PERFORMED?  Yes  No
If 'yes' selected, please fill out remaining questions in this section.
Was a chest x-ray performed?  Yes  No
If yes, please indicate date performed: _____
If yes, do the results support a diagnosis of lower respiratory tract disease (LRTD)?  Yes  No
If LRTD diagnosis supported, further diagnosis by x-ray:  Pneumonia  Other LRTD

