Bundle branch block left
Bundle branch block right
Conduction disorder
Defect conduction intraventricular
Electrocardiogram delta waves abnormal
Lenegre's disease
Long QT syndrome
Paroxysmal atrioventricular block
Sinoatrial block
Trifascicular block
Ventricular dyssynchrony
Wolff-Parkinson-White syndrome
Nodal arrhythmia
Sinus arrest
Sinus arrhythmia
Arrhythmia
Heart rate irregular

Cardiac Arrhythmia (Preferred Terms)
Holiday heart syndrome
Pacemaker generated arrhythmia
Pacemaker syndrome
Paroxysmal arrhythmia
Reperfusion arrhythmia
Withdrawal arrhythmia
Atrial fibrillation
Atrial flutter
Atrial parasystole
Congenital supraventricular tachycardia
Frederick's syndrome
Junctional ectopic tachycardia
Supraventricular extrasystoles
Supraventricular tachyarrhythmia
Anomalous atrioventricular excitation
Cardiac fibrillation
Cardiac flutter
Extrasystoles
Tachyarrhythmia
Cardiac fibrillation
Parasystole
Rhythm idioventricular
Ventricular arrhythmia
Ventricular extrasystoles
Ventricular fibrillation
Ventricular flutter
Ventricular parasystole
Ventricular pre-excitation
Andersen-Tawil syndrome
Arrhythmia neonatal
Arrhythmogenic right ventricular dysplasia
Atrioventricular node dispersion
Brugada syndrome
Foetal arrhythmia
Foetal heart rate disorder
Foetal tachyarrhythmia
Heart block congenital
Junctional ectopic tachycardia
Long QT syndrome congenital
Lown-Ganong-Levine syndrome
Neonatal bradyarrhythmia
Neonatal tachyarrhythmia
Wolff-Parkinson-White syndrome congenital
Baseline foetal heart rate variability disorder
Cardiac arrest neonatal
Cardio-respiratory arrest neonatal
Foetal cardiac arrest
Foetal heart rate acceleration abnormality
Foetal heart rate deceleration abnormality

Renal Impairment (Preferred Terms)
Atypical haemolytic uraemic syndrome
Anuria
Renal failure
Cardiorenal syndrome

Chronic kidney disease
End stage renal disease
Renal impairment
Crush syndrome
Diabetic end stage renal disease
Hepatorenal failure
Foetal renal impairment
Prerenal failure
Haemolytic uraemic syndrome
Hepatorenal syndrome
Nail-patella syndrome
Renal injury
Neonatal anuria
Pancreatorenal syndrome
Postoperative renal failure
Postrenal failure
Renal failure neonatal
Renal impairment neonatal
Scleroderma renal crisis
Subacute kidney injury

X-ray or Radiologic Pneumonia (Preferred Terms)
Eosinophilic pneumonia
Eosinophilic pneumonia acute
Eosinophilic pneumonia chronic
Pneumonitis
Pneumonitis chemical
Idiopathic interstitial pneumonia
Pneumonia
Atypical pneumonia

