COVID-19 pneumonia
Embolic pneumonia
Enterobacter pneumonia
Haemorrhagic pneumonia
Miliary pneumonia
Paraneoplastic pneumonia
Pneumocystis jirovecii pneumonia
Pneumonia
Pneumonia acinetobacter
Pneumonia adenoviral
Pneumonia anthrax
Pneumonia bacterial
Pneumonia blastomyces
Pneumonia bordetella
Pneumonia chlamydial
Pneumonia cryptococcal
Pneumonia cytomegaloviral
Pneumonia escherichia
Pneumonia fungal
Pneumonia haemophilus
Pneumonia helminthic
Pneumonia herpes viral
Pneumonia influenzal
Pneumonia klebsiella
Pneumonia legionella
Pneumonia measles
Pneumonia moraxella
Pneumonia mycoplasmal
Pneumonia necrotising

Pneumonia parainfluenzae viral
Pneumonia pneumococcal
Pneumonia proteus
Pneumonia pseudomonal
Pneumonia respiratory syncytial viral
Pneumonia salmonella
Pneumonia serratia
Pneumonia staphylococcal
Pneumonia streptococcal
Pneumonia toxoplasmal
Pneumonia tularaemia
Pneumonia viral
Pneumonic plague
Post procedural pneumonia
Pulmonary mucormycosis
Pulmonary nocardiosis
Pulmonary paracoccidioidomycosis
Pulmonary sepsis
Pulmonary sporotrichosis
Pulmonary syphilis
Pulmonary trichosporonosis
Pulmonary tuberculosis
Pneumococcal infection
Pneumovirus test positive
Pulmonary tuberculoma

Respiratory Arrest or Failure (Preferred Terms)

Acute respiratory distress syndrome
Acute respiratory failure
Agonal respiration
Apnoea
Apnoeic attack
Bradypnoea
Cardio-respiratory distress
Central-alveolar hypoventilation
Chronic respiratory failure
Hypopnoea
Hypoventilation
Hypoventilation neonatal
Infantile apnoea
Lung hypoinflation
Neonatal respiratory arrest
Neonatal respiratory depression
Neonatal respiratory distress
Neonatal respiratory distress syndrome
Neonatal respiratory failure
Postoperative respiratory distress
Postoperative respiratory failure
Respiratory arrest
Respiratory depression
Respiratory depth decreased
Respiratory distress
Respiratory failure
Respiratory paralysis
Adaptive servo-ventilation
Alveolar oxygen partial pressure abnormal
Alveolar oxygen partial pressure decreased
Alveolar-arterial oxygen gradient increased

Respiratory Arrest or Failure (Preferred Terms)
Anoxia
Asphyxia
Automatic positive airway pressure
Bilevel positive airway pressure
Blood gases abnormal
Capnogram abnormal
Carbon dioxide abnormal
Carbon dioxide increased
Cardiopulmonary failure
Cardio-respiratory arrest
Cardio-respiratory arrest neonatal
Cheyne-Stokes respiration
Chronic respiratory disease
Continuous positive airway pressure
Cyanosis central
Dependence on oxygen therapy

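### As written, the SAP can count pneumonia without imaging as radiologically confirmed, because its complication route is a preferred-term match with no imaging condition

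*SAP*

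**What the plan says.** Protocol 9.4.1.4 lists the endpoint as "First occurrence of pneumonia (radiological or X-ray confirmed) associated with RT-PCR-confirmed RSV-mediated ARIs" and gives no second route. SAP 6.5 keeps the imaging label but names two sources: "First occurrence of pneumonia (radiological or X-ray confirmed, as assessed in the CRF diagnostic tests form or reported as a complication".

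What counts as a complication is set out in SAP 6.4.1.1.2: "See Section 7.8 for the complication terms. These terms will be reported in the AE or the CE domain". That section then turns to form-based sources, saying that asthma and COPD exacerbations from the medically-attended ARI form "will also be counted, as well as X-ray or radiological confirmed pneumonia from the diagnostic tests form".

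The relevant list in SAP Appendix 8 is headed "X-ray or Radiologic Pneumonia (Preferred Terms". It consists of MedDRA terms, among them plain *Pneumonia*, *Pneumonia viral*, *Pneumonitis*, *Pneumococcal infection* and "Pneumovirus test positive".

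Imaging results are collected separately. The medically-attended ARI form (protocol Appendix 6) follows the chest X-ray question with "If LRTD diagnosis supported, further diagnosis by x-ray", with pneumonia or other LRTD as the choices. It has matching items for CT and MRI in patients seen in an emergency department or admitted.

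**The concern.** An endpoint labelled imaging-confirmed should contain only events with an imaging finding. A preferred term records a diagnosis, not how it was reached. Two participants whose events code to *Pneumonia*, one with a positive chest film and one diagnosed at the bedside, look the same to a program that matches terms.

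Two things are at stake. The first is labelling: the count and the vaccine efficacy (VE) would be read as referring to radiologically confirmed disease when they refer to a mixture. The second is specificity: if VE against confirmed pneumonia differs from VE against the RSV ARIs that carry an unconfirmed diagnosis, the estimate moves towards the latter. The same list also reaches further than the stand-alone endpoint, because it defines one way to qualify for predefined clinically relevant disease, confirmatory secondary endpoint 4 in protocol 9.4.1.3.

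**Working it through.** The plan gives no figure to reproduce, so the check sets the rules side by side.

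1. **Protocol endpoint (9.4.1.4).** Imaging confirmation is part of the definition.
2. **SAP endpoint (6.5).** Same label, two sources. Taken alone, the sentence can mean imaging-confirmed pneumonia recorded in either place, or imaging-confirmed pneumonia plus any pneumonia complication.
3. **SAP complication rule (6.4.1.1.2).** Terms are matched in the AE or CE data. No imaging variable enters the rule. Pneumonia from the diagnostic tests form is counted in addition, so the form widens the set and does not restrict it.
4. **Term list (Appendix 8).** Only the heading mentions imaging. Plain *Pneumonia* says nothing about it, and "Pneumovirus test positive" is a laboratory result. In SAP 6.10.2 the same plain term defines an adverse event of clinical interest with no suggestion of imaging.
5. **Data capture (protocol 1.3.2, footnote l).** Sites record complications, pneumonia among them, with no imaging qualifier.
6. **Declared changes (SAP Appendix 2).** The added route is not listed as a departure from the protocol.

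Steps 3 and 4 resolve the ambiguity in step 2: a programmer following the SAP would count a linked event coded to *Pneumonia* whether or not a film was taken.

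**Reach.** Protocol 8.2.3 names imaging-confirmed pneumonia as the qualifying complication for clinically relevant disease. The SAP implements it with the same list. SAP 6.11 keeps clinically relevant disease in the reduced final analysis and does not list stand-alone pneumonia.

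**Illustration only.** Every input here is an assumption. Let *s* be the share of counted placebo cases without imaging.

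- Pooled VE = (1 − *s*) × VE(confirmed) + *s* × VE(unconfirmed).
- With 80% and 60%: *s* = 0.2 gives 0.8 × 80 + 0.2 × 60 = 76%; *s* = 0.5 gives 0.5 × 80 + 0.5 × 60 = 70%.
- With 80% and 69.8%, the highest and lowest LRTD estimates that protocol 2.2 reports from the phase 2b study: 0.8 × 80 + 0.2 × 69.8 = 78.0%, and 0.5 × 80 + 0.5 × 69.8 = 74.9%.
- With equal efficacies the shift is zero.
- The placebo count exceeds the confirmed count by 1/(1 − *s*), which is 1.25-fold to 2-fold. Under the 80%/60% assumption the vaccine-arm ratio is (0.8 × 0.2 + 0.2 × 0.4)/(0.8 × 0.2) = 0.24/0.16 = 1.5 at *s* = 0.2, and (0.5 × 0.2 + 0.5 × 0.4)/(0.5 × 0.2) = 0.30/0.10 = 3 at *s* = 0.5.

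These lines show how the answer depends on the inputs. They do not estimate what happened in the trial.

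**The case against.** The best defence is that the complication is itself defined as imaging-confirmed. Protocol 8.2.3 says so, and the Appendix 8 heading repeats it. The CRF complication page is not among the documents and may ask for imaging. That is possible and cannot be ruled out. But the SAP rule does not refer to such an item, it also draws terms from the AE data, and a heading does not filter records.

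It is also true that the protocol is not uniform. The objectives and endpoints table in section 3 lists pneumonia without a qualifier, and only 9.4.1.4 adds imaging. So the conflict is with 9.4.1.4 and, for the composite, with 8.2.3, not with every mention in the protocol.

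On consequence, the objection largely stands for stand-alone pneumonia. The endpoint is exploratory, outside the testing strategy, and not on the SAP 6.11 list. Events will be few: the planned incidences imply 0.2% × 7,670 ≈ 15 to 0.5% × 7,670 ≈ 38 placebo LRTD cases per season before exclusions, and presumably fewer pneumonias. With an assumed 10 placebo and 4 vaccine cases at 2:1, VE is 80% and the exact 95% interval is about 31% to 95%, wide against a shift of a few points. For the composite, a participant with pneumonia may qualify by another route, such as hospitalization, an emergency visit or supplemental oxygen.

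A reader might infer that any pneumonia at all is counted. The documents do not support that: the event must code to an Appendix 8 term and be linked to the ARI.

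**Conclusion.** The point holds as a defect of definition and labelling. Under the SAP as written, a pneumonia without imaging that codes to an Appendix 8 term can be counted as imaging-confirmed, against protocol 9.4.1.4. The same applies to the pneumonia component of clinically relevant disease, against protocol 8.2.3, to the extent that a listed pneumonia term is a participant's only qualifying criterion.

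The size is unknown. Neither document gives the number of pneumonias with and without imaging, or how often the term alone qualifies a participant for the composite.

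Two stronger readings are tempting. One is that the reported VE is lowered, or the confirmed count inflated, by a stated amount; that would rest wholly on assumed shares and efficacies. The other is that error control for secondary endpoint 4 is compromised; nothing in the documents shows that, since the same rule applies to both arms in a blinded comparison. The conclusion assumes that the SAP is programmed as written and that no imaging item on the complication page acts as an unstated filter.

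**What to change.** - Count an Appendix 8 pneumonia term as imaging-confirmed only if a linked X-ray, CT or MRI record supports it, from the diagnostic tests form, the medically-attended ARI form, or an imaging item on the complication page if there is one.
- Report imaging-confirmed pneumonia and any reported pneumonia as separate rows.
- Rename the Appendix 8 list simply Pneumonia, and remove terms that are not pneumonia, such as "Pneumovirus test positive".
- Apply the same rule to the pneumonia component of clinically relevant disease, or record the wider definition in SAP Appendix 2 as a change from the protocol.

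The cost is SAP wording and a link between forms already collected. Confirmed events will be fewer and the interval wider. Some truly imaged cases may drop out where a form completed by an outside provider is missing; the any-reported row keeps them visible.
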